11.4 Event Relationship

The following definitions will be used to assess the relationship of the adverse event to the investigational medical device/study procedure(s):

Not related: Relationship to the device, comparator or procedures can be excluded when:

- the event has no temporal relationship with the use of the investigational device, or the procedures related to application of the investigational device;
- the (serious) adverse event does not follow a known response pattern to the medical device (if the response pattern is previously known) and is biologically implausible;
- the discontinuation of medical device application or the reduction of the level of activation/exposure - when clinically feasible - and reintroduction of its use (or increase of the level of activation/exposure), do not impact on the (serious) adverse event;
- the event involves a body-site or an organ that cannot be affected by the device or procedure;
- the (serious) adverse event can be attributed to another cause (e.g. an underlying or concurrent illness/ clinical condition, an effect of another device, drug, treatment or other risk factors);
- the event does not depend on a false result given by the investigational device used for diagnosis, when applicable;

In order to establish the non-relatedness, not all the criteria listed above might be met at the same time, depending on the type of device/procedures and the (serious) adverse event.

Possible: The relationship with the use of the investigational device or comparator, or the relationship with procedures, is weak but cannot be ruled out completely. Alternative causes are also possible (e.g. an underlying or concurrent illness/ clinical condition or/and an effect of another device, drug or treatment). Cases where relatedness cannot be assessed, or no information has been obtained should also be classified as possible.

Probable: The relationship with the use of the investigational device or comparator, or the relationship with procedures, seems relevant and/or the event cannot be reasonably explained by another cause.

Causal relationship: the (serious) adverse event is associated with the investigational device, comparator or with procedures beyond reasonable doubt when:

- the event is a known side effect of the product category the device belongs to or of similar devices and procedures;
- the event has a temporal relationship with investigational device use/application or procedures;
- the event involves a body-site or organ that
 - the investigational device or procedures are applied to;
 - the investigational device or procedures have an effect on;
- the (serious) adverse event follows a known response pattern to the medical device (if the response pattern is previously known);
- the discontinuation of medical device application (or reduction of the level of activation/exposure) and reintroduction of its use (or increase of the level of activation/exposure), impact on the (serious) adverse event (when clinically feasible);
- other possible causes (e.g., an underlying or concurrent illness/ clinical condition or/and an effect of another device, drug or treatment) have been adequately ruled out;
- harm to the subject is due to error in use;
- the event depends on a false result given by the investigational device used for diagnosis, when applicable;

In order to establish the relatedness, not all the criteria listed above might be met at the same time, depending on the type of device/procedures and the (serious) adverse event.

11.5 Adverse Event Reporting

Subjects will be carefully monitored during the study for possible adverse events. Safety will be assessed by collecting adverse event/device deficiency data on each patient and will be captured in the CRFs. Any adverse event/device deficiency occurring since subject signed ICF will be recorded in the subject's CRF.

Note: Any medical condition that is present at the time that the subject is screened will be considered as baseline and not reported as an adverse event further in the study. However, if that subject's condition deteriorates at any time during the study, it will be recorded as an AE.

Appropriate treatment will be initiated and the study follow-up will continue as completely as possible.

Planned hospitalization for a pre-existing condition, or a procedure required by the CIP, without serious deterioration in health, is not considered a Serious Adverse Event.

Out of range (abnormal) laboratory value(s) should be captured as an AE(s) if clinically significant.

Ongoing AE should be reviewed and updated at each visit, if applicable. AE will continue to be recorded throughout the study including the follow-up until study exit.

The Investigator will document all observations and clinical findings of adverse events, including the nature, date of onset and stop date (if applicable), severity, seriousness, action(s) taken/treatment, outcome and relationship to the investigational medical device/study procedure(s), on the appropriate eCRFs in the EDC. Whenever possible, available source documentation should be provided to the Sponsor.

The Investigator is required to report Adverse Events/Device Deficiencies to the Sponsor within the following timeframes:

Type of event	Timeline for Reporting
SAE/SADE/UADE/ASADE/USADE	Immediately, but not later than 3 calendar days after investigation site study personnel's awareness of the event
All other AEs/ADEs	In a timely manner, usually within 7 calendar days after investigation site study personnel's awareness of the event
Device Deficiency	Immediately, but not later than 3 calendar days after investigation site study personnel's awareness of the event
Serious Health Threat	At the earliest possible opportunity, but not later than within 24 hours after investigation site study personnel's awareness of the event

Emergency contact for safety reporting:

CRO company:

Safety Department

E-mail: [contact]

Sponsor: Neptune Medical

E-mail: [contact]

As additional information concerning AEs/DDs becomes available, the Investigator will record it on the appropriate CRFs. Copies of source documentation which contain significant information related to the event such as progress notes, consultations, nurse's notes, operative reports and patient summaries etc. are required for evaluation of the event. Copies of such documentation shall be obtained from the Investigator (de-identified as to the Subjects' identity) and provided to the Sponsor.

Regarding Subject deaths, it is requested that a copy of the death certificate and a copy of the autopsy report, if applicable, be sent to the Sponsor when available. Any other source documents related to the death should also be provided to the Sponsor. In the event that no source documents are available, the PI is required to describe the circumstances of the Subject's death in a letter, e-mail, or other written communication.

The Sponsor will comply with Medical Device Regulation (MDR) reporting requirements.

Reportable events will be reported to the applicable Regulatory Bodies of participating countries according to applicable local and national regulations.

In general, safety reporting to the Regulatory Bodies in European Economic Area (EEA) will be performed in accordance with MDCG 2020-10/1, unless specified otherwise.

The summary is provided below:

- the following events are considered reportable events in accordance with MDR Art. 80(2):
 - a) any Serious Adverse Event that has a causal relationship with the investigational device, the comparator or the investigation procedure or where such causal relationship is reasonably possible;
 - b) any Device Deficiency that might have led to a Serious Adverse Event if appropriate action had not been taken, intervention had not occurred, or circumstances had been less fortunate;
 - c) any new findings in relation to any event referred to in points a) and b).
- Reporting to the applicable Regulatory Bodies to be performed within the following timeframes:
 - a) for all reportable events which indicate an imminent risk of death, serious injury, or serious illness and that requires prompt remedial action for other patients/subjects, users or other persons or a new finding to it: Immediately, but not later than 2 calendar days after awareness by sponsor of a new reportable event or of new information in relation with an already reported event.
This includes events that are of significant and unexpected nature such that they become alarming as a potential public health hazard. It also includes the possibility of multiple deaths occurring at short intervals.

- b) Any other reportable events or a new finding/update to it: Immediately, but not later than 7 calendar days following the date of awareness by the sponsor of the new reportable event or of new information in relation with an already reported event.

12. STUDY ADVISORS

The Study will utilize National Principal Investigators (NPIs) as advisors to provide study leadership and guidance. The NPIs will oversee all clinical study activities including clinical investigation plan development or any changes that may be desired or required during the conduct of the Study. The NPIs will also assist in obtaining evaluation and feedback from peers throughout the course of the Study. The Study will have two NPIs who will oversee all clinical study activities.

12.1 Imaging Core Laboratory

Medical Metrics Inc is the Core Lab designated for the SPIRARE I Clinical Study. The objectives of the Core Lab are to provide an unbiased assessment of the RV/LV ratio.

For each Subject treated with the Vertex Pulmonary Embolectomy System, the investigational site will be instructed to follow a standard procedure developed by the Core Lab for obtaining study specific angiographic images. CT imaging studies will be obtained at baseline and 48 hours (± 8 hours) follow-up.

Images will be sent directly from the site to the Core Lab. Core Lab definitions and procedures will be documented in the Core Lab Manual of Operations (MOP) and CRFs.

13. STATISTICAL DESIGN AND METHODS

13.1 Analysis Populations

The populations are defined as follows:

An enrolled patient is defined as all patients who met the inclusion/exclusion criteria and who provide written informed consent, meet the inclusion/exclusion criteria, and in whom the Vertex Catheter is introduced past the pulmonic valve.

The Intent-To-Treat (ITT) population is defined as all enrolled patients who met the inclusion/exclusion criteria and who provide written informed consent, and in whom the Vertex Catheter is introduced past the pulmonic valve; when Vertex Catheter is introduced past the pulmonic valve, and in whom the Vertex Pulmonary Embolectomy System is not able to access a pulmonary embolus.

All enrolled and ITT patients will be monitored per clinical investigation plan until the end of the required follow up period of 30 days.

This is a prospective, multicenter, single arm study designed to evaluate the safety and efficacy of the Vertex Pulmonary Embolectomy System for the aspiration of clot in patients with acute PE. The efficacy analysis will be conducted in the Intent-to-treat and per clinical investigation plan populations and the safety analysis will be conducted in all patients (enrolled, ITT, and procedural screen failures).

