Event Severity	Mild	No limitation of usual activities, no therapy or only symptomatic therapy required to treat the injury or illness.
Event Severity	Moderate	Some limitation of usual activities or specific therapy is required.
Event Severity	Severe	Inability to carry out usual activities, hospitalization, emergency room treatment, life-threatening events, or death.
Injury	Cardiac Injury	Cardiac injury is defined as any damage to the heart requiring intervention to avoid permanent injury. Examples of possible cardiac injury : Acute heart failure • Acute myocardial infarction • Arrhythmia requiring intervention • Cardiac hematoma • Tricuspid or Pulmonic valve damage
Injury	Pulmonary Vascular Injury	
Pulmonary vascular injury is defined as perforation or injury of a major pulmonary arterial branch requiring intervention to avoid permanent injury.
 
Examples of possible pulmonary vascular injury: Arterial Venous Fistula • Dissection • Hemorrhage • Intimal flap • Perforation • Rupture • Thromboembolic occlusion resulting in permanent damage i.e. infarction

Study Population	Operative Screen Failure	Any eligible patient in whom the Vertex Catheter is not attempted or placed for any reason. Up until this point, the procedure may be converted to another therapeutic treatment or discontinued without the patient receiving any investigational treatment.
Study Population	Intent to Treat (ITT)	All patients who provide written informed consent, meet the inclusion/exclusion criteria, and in whom the Vertex Catheter is introduced past the pulmonic valve; enrollment occurs when Vertex catheter is introduced past the pulmonic valve. Any patient enrolled into the trial, but in whom the Vertex Pulmonary Embolectomy System is not able to access a pulmonary embolus is considered an Intent to Treat patient
Study Population	Screen Failure	Any screened patient who signs the ICF but does not meet the inclusion and exclusion criteria.

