2.6 Enrollment

Patients that fit the inclusion/exclusion criteria and provide written informed consent to participate in the study will be enrolled on intent to treat basis (ITT). An enrolled patient is defined as all patients who met the inclusion/exclusion criteria and who provide written informed consent, meet the inclusion/exclusion criteria, and in whom the Vertex Catheter is introduced past the pulmonic valve. The study will continue to enroll subjects until there are 10 (ten) enrolled and treated subjects.

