2.8 Subject Screening

Patients will be screened to determine their initial eligibility and interest in the study. in the Inclusion/Exclusion criteria. Informed consent will be obtained once a patient has satisfied screening criteria and prior to any study-specific procedures that are not part of the standard of care. All patients screened will be documented on the Screening/Enrollment Log.

Medical Screen failures will be defined as follows

- **Screen Failure:** Any screened patient who signs the ICF but does not meet all the inclusion or meets any of the exclusion criteria and also such who signed ICF but for whom the Vertex catheter was not introduced and past the pulmonic valve. All patients screened will be documented on the Screening/Enrollment Log. The reason for screen failure will be captured on the log and in the screening/enrollment section of the database. For operative screen failures please refer to section 5.1. for further details.

For Procedural screen failure definitions please refer to *section 5.1*

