5.1.2 Operative Screen Failures

The following subjects are considered operative failures:

- Any eligible patient in whom the Vertex Catheter is not able to be introduced into the pulmonary artery for any reason.
- Until any point prior to the introduction of the Vertex Pulmonary Embolectomy System, the procedure may be converted to another therapeutic treatment or discontinued without the patient receiving any investigational treatment.

No further information will be collected on this patient; a study exit form (CRF) is required for all these patients. Any patient that experiences an adverse event after venous puncture but in whom the Vertex Catheter is not inserted will be monitored through discharge for safety and information about AEs will be collected in CRF, if applicable.

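### Enrolled and ITT status depend on having met the eligibility criteria, so a treated patient later found ineligible is outside ITT and outside every group listed for the safety analysis

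*Combined protocol and SAP*

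**What the plan says.** **Enrolled and ITT.** Section 13.1: "An enrolled patient is defined as all patients who met the inclusion/exclusion criteria and who provide written informed consent", with the further condition that the catheter has passed the pulmonic valve. Section 2.6 uses the same definition ("An enrolled patient is defined as all patients who met the inclusion/exclusion criteria"). For ITT, 13.1 says "The Intent-To-Treat (ITT) population is defined as all enrolled patients who met the inclusion/exclusion criteria"; 5.1.3 and the entries in the Abbreviations and Terms tables carry the same eligibility condition.

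**Screen Failure.** Section 2.8: "Any screened patient who signs the ICF but does not meet all the inclusion or meets any of the exclusion criteria". It then adds, as a separate limb, consented patients in whom the catheter did not pass the valve. The Terms table: "Any screened patient who signs the ICF but does not meet the inclusion and exclusion criteria".

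**Procedural screen failure.** Section 5.1.1 covers access failures in which the system is not used. Section 5.1.2 covers "Any eligible patient in whom the Vertex Catheter is not able to be introduced into the pulmonary artery for any reason".

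**Analysis sets.** Efficacy is analysed in the ITT and per-clinical-investigation-plan populations; 13.1 does not define the latter. For safety, "the safety analysis will be conducted in all patients (enrolled, ITT, and procedural screen failures" is the whole of the list.

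**Follow-up.** Section 13.1: "All enrolled and ITT patients will be monitored per clinical investigation plan until the end of the required follow up period of 30 days"; 5.1.3 gives the same period for ITT patients. Section 2.3 describes participation of up to 30 days after treatment for each study Subject, 2.2 gives a Subject number to everyone who consents, and 11.5 records adverse events from consent to study exit.

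**Numbers.** Section 2.1 expects at most 10 Subjects. Section 2.6 continues until 10 are both enrolled and treated. Section 13.2 plans descriptive summaries only.

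**The concern.** In a single-arm study of an investigational device, exposure to the device should decide who is in the safety set. Here an eligibility ruling decides it, and nothing says that the ruling is closed once the patient has been treated. If a breach surfaces later, for instance through a misread laboratory value or a symptom date corrected at monitoring, the definitions move a fully treated patient into a screening category. Meanwhile patients who never received the device are named in the safety set.

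The plan's own criteria make such a dispute possible. Symptom duration is at most 14 days in the synopsis and in sections 2 and 2.4, but less than 14 days in 2.9. The heart-rate exclusion includes 130 beats per minute in the synopsis but not in 2.10. A patient exactly at either limit is eligible under one passage and ineligible under another. These passages need reconciling in their own right.

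With about 10 patients and a descriptive analysis, the observed count is the result, so a rule that can add or remove one patient matters.

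**Working it through.** The plan states no figure to reproduce on this point, so the check applies its definitions to one case: a patient who consented, had the catheter past the pulmonic valve, and was afterwards found to breach a criterion.

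| Category | Source | Does this patient belong? |
|---|---|---|
| Enrolled | 2.6, 13.1 | No: criteria not met |
| ITT | 5.1.3, 13.1 | No: subset of enrolled |
| Access failure | 5.1.1 | No: the system was used |
| Operative screen failure | 5.1.2 | No: not eligible, and the catheter was placed |
| Screen Failure | 2.8, Terms table | Yes: consented and ineligible |
| Groups listed for safety | 13.1 | None of the three |
| Adverse event recording | 11.5 | Yes: consent to study exit |
| 30-day monitoring rule | 5.1.3, 13.1 | Not named; 2.2, 2.3 and 11.5 point the other way |

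Because 2.8 lists non-use of the device as a separate limb, its ineligibility limb does not itself require that the device was unused.

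**Size (assumed case).** One treated patient is later found ineligible and has a Major Adverse Event; no other treated patient has one. Intervals are exact (Clopper–Pearson) 95% and only show scale, since the plan specifies none. With no events, the upper limit is 1 − 0.025^(1/n).

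*Patient replaced, as 2.6 implies (10 eligible treated patients plus this one):*
- Every treated patient counted: 1/11 = 9.1% (0.2–41.3%).
- Only the listed groups: 0/10 = 0%, upper limit 1 − 0.025^(1/10) = 30.8%.

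*Patient not replaced, for example because the maximum in 2.1 blocks it:*
- Every treated patient counted: 1/10 = 10% (0.3–44.5%).
- Only the listed groups: 0/9 = 0%, upper limit 1 − 0.025^(1/9) = 33.6%.

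Replacement means treating an 11th patient, which conflicts with the maximum of 10 in 2.1.

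**How often.** The documents give no rate. If the chance q that a treated patient is later found ineligible is assumed, the chance of at least one among 10 is 1 − (1 − q)^10: 18% for q = 2%, 40% for q = 5% and 65% for q = 10%.

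**The case against.** The strongest reply is that the plan is silent on late-found ineligibility, and silence is not a rule to exclude. Section 5 places the eligibility check before the procedure, and 2.8 sits under screening, so its definition reads naturally as a state before device use. Several criteria are determined by the site, so a differing core-laboratory reading alone would not make a patient ineligible. Section 9.8 defines deviations broadly enough to cover treating an ineligible patient. The drafting is also loose: taken literally, the ITT sentence in 13.1 admits only patients whose embolus could not be reached, so close reading of it is weak ground.

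Part of this stands. A reader might infer that the patient's harms definitely leave the safety analysis. The documents do not support that: 13.1 says all patients before its bracket, 13.2 promises summaries of all safety and efficacy data, and 11.5 keeps the events recorded. A reader might also infer that 30-day follow-up is not required. Sections 2.2, 2.3 and 11.5 support follow-up, and 9.7.2 does not give late-found ineligibility as a reason for withdrawal.

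What does not stand is that the gap closes. The eligibility condition recurs in the Abbreviations and Terms tables, 2.6, 5.1.3 and 13.1, so it is not a stray phrase. The bracket is the only list of safety groups, and recording an event does not put the patient in a denominator. Nothing in 13.1 or 13.2 restores the patient to ITT.

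**Conclusion.** The point holds in a limited form. As written, a treated patient later found ineligible is outside ITT, and so outside the ITT efficacy analysis. The undefined per-plan population does not secure a place for this patient either. The patient is also in none of the three groups named for safety; the all-patients wording permits inclusion but does not settle it. On follow-up, the conclusion is only that the passages disagree and must be reconciled.

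The size, 1/11 against 0/10, rests on the assumed case and on reading the safety bracket as exhaustive. The 1/10 to 0/9 comparison applies only if the patient is not replaced. No pre-set decision would change, because the plan has no hypothesis test or performance goal.

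A reader might further infer that the rule favours the device because ineligible patients are likelier to be harmed. The documents give no evidence for that direction. The objection is one of principle: membership of the set should not depend on an eligibility ruling that could be made after the outcome is known. This is a should-fix point.

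**What to change.** 1. In 2.6, 5.1.3, 13.1 and the Abbreviations and Terms tables, define enrolled, ITT and the safety set by consent plus device use (catheter past the pulmonic valve), regardless of eligibility. Keep procedural screen failures in the safety set.
2. In 2.8 and the Terms table, limit Screen Failure to patients without device use.
3. In 9.8 and 13.1, classify ineligibility found after device use as a plan deviation that removes the patient only from the per-clinical-investigation-plan set, and define that set.
4. State that the existing 30-day follow-up applies to every treated patient, so that 2.3, 5.1.3, 11.5 and 13.1 agree.
5. Reconcile the maximum of 10 in 2.1 with the stopping rule in 2.6 under the new definition.

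The cost is wording only: no extra procedures, and no extra patients beyond those the plan already allows. The drawback is that a treated ineligible patient counts in the headline result, which may look slightly less favourable. The change should be made before outcomes are known.

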2.1 Number of Sites and Subjects

A maximum of 2 sites will participate in the Study. The total population for the Study is expected to be a maximum of 10 Subjects.

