5.1.3 Intent-To-Treat (ITT)

The Intent-To-Treat (ITT) population is defined as all enrolled patients who met the inclusion/exclusion criteria and who provide written informed consent, and in whom the Vertex Catheter is introduced past the pulmonic valve; when Vertex Catheter is introduced past the pulmonic valve, and in whom the Vertex Pulmonary Embolectomy System is not able to access a pulmonary embolus and will be monitored per clinical investigation plan until the end of the required follow up period of 30 days.

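### The ITT definition in 13.1 and 5.1.3, read literally, admits only patients whose embolus could not be reached, and so contradicts the inclusive definition in the abbreviations and terms tables

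*Combined protocol and SAP*

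**What the plan says.** Section 13.1 sets out the analysis populations. Its ITT sentence starts from all enrolled patients who met the entry criteria, consented and had the catheter past the pulmonic valve. It then repeats the valve condition in a dangling *when* clause and continues: "and in whom the Vertex Pulmonary Embolectomy System is not able to access a pulmonary embolus". Section 5.1.3 has the same construction: "and in whom the Vertex Pulmonary Embolectomy System is not able to access a pulmonary embolus and will be monitored per clinical investigation plan".

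The abbreviations table and the terms table define ITT in two separate sentences. The first covers all eligible, consented patients with the catheter past the valve and adds that "enrollment occurs when Vertex catheter is introduced past the pulmonic valve". The second says that an enrolled patient in whom the system "is not able to access a pulmonary embolus is considered an Intent to Treat patient". Section 2.3 also describes enrolment as being on an ITT basis.

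On use of the sets, 13.1 says: "The efficacy analysis will be conducted in the Intent-to-treat and per clinical investigation plan populations". It names neither as primary and does not define the second. Safety is to be analysed in all patients, followed by a parenthesis listing enrolled, ITT and procedural screen failures.

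On numbers, section 2.1 says: "The total population for the Study is expected to be a maximum of 10 Subjects". Section 2.6 says: "The study will continue to enroll subjects until there are 10 (ten) enrolled and treated subjects".

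**The concern.** The section that governs the analysis states a rule that, followed as written, would summarise RV/LV reduction only in patients whose clot was never reached, or in nobody. The tables at the front give a different population, and the plan states no order of precedence. Section 13.1 also mentions enrolled and ITT patients side by side as if they were different groups, which fits the restrictive wording.

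Descriptive summaries are this study's whole statistical output, so the choice of denominator is the main analytical decision. If the conflict stays open, that choice could be made after about ten outcomes are known. The same section leaves it unclear whether every exposed patient is in the safety set, and 2.6 leaves it unclear when enrolment stops.

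**Working it through.** The plan gives no sample-size or power figure to reproduce: the number is a cap of 10, and 13.2 plans descriptive statistics only. The check is therefore a comparison of texts, followed by set sizes.

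**Step 1. The ITT definitions side by side.**

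| Place | Rule as worded | Size with *E* enrolled and *F* access failures |
|---|---|---|
| Abbreviations and terms tables | past the valve; failures also count | *E* |
| 5.1.3 and 13.1 | past the valve **and** embolus not accessed | *F* |

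The sentence in 5.1.3 and 13.1 reads like the two table sentences run together. The main clause about when enrolment occurs has gone, leaving a dangling *when*, and so has the opening of the second sentence, which made access failures an addition. What was an addition has become a condition.

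**Step 2. Size of the difference at *E* = 10.** With *F* = 1, the sets have 1 and 10 patients. With *F* = 0, they have 0 and 10.

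The documents give no embolus-access rate for this device. As an assumption, let the rate *a* run from 80% to 99%. The range includes 86.5%, the technical success rate in Table 2 for a meta-analysis of other catheter techniques in high-risk PE. The expected literal ITT size is 10(1 − *a*), and the probability that it is empty is *a*^10.

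| Assumed access rate | Expected literal ITT | P(literal ITT empty) | Inclusive ITT |
|---|---|---|---|
| 80% | 2.0 | 0.107 | 10 |
| 86.5% | 1.35 | 0.234 | 10 |
| 90% | 1.0 | 0.349 | 10 |
| 95% | 0.5 | 0.599 | 10 |
| 99% | 0.1 | 0.904 | 10 |

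**Step 3. Effect on the RV/LV summary (illustration).** Assume that reached patients average a reduction of 0.38, the Table 2 figure for the 2019 aspiration study, and that one failure shows no change. The literal ITT mean is 0.00. The inclusive ITT mean is (9 × 0.38 + 0)/10 = 0.342.

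**Step 4. The safety set.** Both the enrolled and the ITT definitions require that the entry criteria were met. A patient who was treated and later found ineligible is in neither. That patient is not a procedural screen failure either, since 5.1.1 and 5.1.2 cover failed access and failure to get the catheter into the pulmonary artery. By its wording, section 2.8 would class the patient as a medical screen failure. So none of the three groups in the 13.1 parenthesis holds this patient, although the words before it say all patients.

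**Step 5. When enrolment stops.** Enrolled already means that the catheter is past the valve. If *treated* adds nothing, enrolment stops at 10 and 2.6 agrees with 2.1. If *treated* leaves out an access failure, one failure takes enrolment to 11, above the maximum. The word is not defined.

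**The case against.** The strongest reply is that the intended meaning can be recovered. Two tables give the inclusive definition, 2.3 enrols on an ITT basis, and the 13.1 sentence itself begins with all enrolled patients and is visibly garbled. Section 13.2 plans no test and says that summaries use all observed data at each visit, so no success criterion or error rate depends on the set. This stands, and it limits the weight of the point. It does not remove it: the section that specifies the analysis still states the wrong rule, and its other efficacy set has no definition to fall back on.

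A reader might infer three stronger things that the documents do not support:

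- *That the primary effectiveness population is the failures alone.* The tables contradict this, and 13.1 calls neither efficacy set primary.
- *That access failures are replaced, which flatters the result.* No section says that such a patient is untreated or replaced, and the synopsis and 2.1 both cap the total at ten. Even if enrolment reached 11, the inclusive ITT would keep the failure; in the illustration above the mean would be (10 × 0.38 + 0)/11 = 0.345. A flattering figure needs a treated-only analysis set, and 13.1 does not name one.
- *That an ineligible treated patient drops out of the safety analysis.* The words all patients point the other way, and section 11.5 records every adverse event from consent onward. The parenthesis only makes the exclusion possible to read.

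**Conclusion.** The point holds as an internal contradiction. Sections 5.1.3 and 13.1 literally restrict ITT to access failures, while the abbreviations and terms tables include all eligible, consented patients past the pulmonic valve. At full enrolment the two readings give *F* patients, possibly none, against 10. The cause appears to be a drafting merge, and the inclusive reading is very probably what was meant. It still needs correcting, because 13.1 governs the efficacy summaries and leaves the per-plan set undefined.

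The safety parenthesis and the word treated in 2.6 are ambiguities to close, not demonstrated errors. The consequence is confined to descriptive summaries in about 10 patients. The set sizes for given *E* and *F* follow from the wording alone; the access rates and the RV/LV illustration are assumptions.

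**What to change.** 1. In 5.1.3 and 13.1, replace the ITT text with: *all enrolled patients, that is, every consented patient whose Vertex Catheter crosses the pulmonic valve, whether or not the system then reaches an embolus*. Name this set as primary for the RV/LV endpoint.
2. Align the enrolled definition in 2.6, 13.1 and the two tables with this, so that meeting the entry criteria is a condition for starting treatment and not for being counted afterwards. Without this step the new ITT text would still exclude a treated patient later found ineligible.
3. State that the safety set is every patient in whom the device was introduced, whether or not later found ineligible, plus procedural screen failures.
4. Reconcile 2.6 with 2.1 so that the count of 10 refers to enrolled patients, and delete or define *treated*.
5. Define the per-plan set consistently with section 5.2. That section labels clot-reducing adjuncts as treatment failures and does not count thrombolytics given for clinical deterioration as a deviation. The definition should respect both statements, and treatment failures should stay in the primary efficacy summary.

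The cost is a wording amendment, with no added patients or procedures. The mean RV/LV reduction may come out slightly less favourable because access failures and treatment failures stay in.
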